4.7 Follow-up and study end points

Patients will be followed up weekly for 8 weeks or until ulcer completely heals, whichever is earlier. The complete healing of ulcer will be determined clinically as complete closure of epithelium of the skin which will be photographed for verification. In the event that study participants develop any complications such as worsening of existing ulcer, skin abrasions due to friction or sever swelling to the foot or leg, they may be considered as censored if it affects the wearing of the off-loading device and will not be continued for follow-up. Such patients will be referred to The Leprosy Mission Trust India tertiary hospital at Champa in India and Anandaban Hospital in Nepal for further evaluation and treatment.

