1.8 Outcomes

The main outcome measures are; 1) Adherence to removable walker boot which will be measured using pedometer; one placed inside the walker boot and second on patient's wrists as a watch/ in pocket. 2) User satisfaction which will be measured using standard questionnaire. 3) Ulcer healing which we will measure the healing of ulcer time to (complete epithelisation of ulcer) and measure the rate of healing both assessed from photographs by masked observers.

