4.6.3 Randomization and allocation

Participants will be enrolled sequentially, and randomly allocated (1:1) to receive removable walker boot or MCR using the "digital sealed envelope" method resident in a computer. An allocation table will be generated remotely by the trial statistician at the George Institute of Global Health India. A permuted block random method will be used to generate the randomization sequence within each stratum.

Randomly selected blocks of size 2, 4, 6, or 8 will be generated to maintain balance between the numbers allocated to each of the two groups and to ensure allocation concealment. The generated table will be uploaded into the REDCap software to be used for participant enrolment. Access to the allocation table will be restricted. Trial staff in India and Nepal will not have access to the allocation table. When a participant's details are submitted, the trial arm and a unique study number will be assigned and revealed to the local clinician so that the randomized group that the participant is assigned to cannot be

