4.6.5 Main outcome measures

- 1. Adherence to removable walker boot: Adherence will be measured using pedometer; one placed inside the walker boot and second on patient's wrists as a watch/ in pocket. The pedometer will provide data on number of steps taken by patient during the assessment period which will be recorded weekly. We will compare the groups based on their steps per day. In addition, the difference in cumulative steps recorded between the two pedometers will provide a further measure the compliance to walker boot. We will measure the difference in the difference between intervention and control.
- User satisfaction: We will measure the user satisfaction with the off-loading devices using the Quebec User Evaluation of Satisfaction with Assistive Technology (QUEST) 2.0 at complete healing of ulcer or at 8 weeks from recruitment, whichever is earlier.
- 3. Ulcer healing: We will measure the healing of ulcer time to (complete epithelisation of ulcer) and also measure the rate of healing. All observations will be based on 'blind' assessment. The patient will be followed up for 8 weeks and photographs of ulcers will be taken at baseline and after every 2 weeks until the ulcer heals or at 8 weeks, whichever is earlier, to measure the ulcer area. The ulcer will be measured from the photographs taken using the data collection tablets. The ulcer will

altered.

be measured by masked observers in another site using the PUSH (Pressure Ulcer Scale for Healing) tool with which we have considerable experience.

The photographs of the ulcer will be taken using standard and uniform method in both the study sites. Photographs will be taken in a well-lit area in a long sitting position with the foot elevated slightly on soft material. The image of the ulcer will be captured by the research assistant standing directly in front of the patient with the camera placed parallel to the affected foot/ulcer.

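### The summary and outcome sections give the healing outcome to masked photograph readers, but section 4.7 has complete healing determined clinically; that event ends follow-up, and the protocol does not say whose reading prevails.

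*Protocol*

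**What the plan says.** **Masked reading.** Section 1.8 lists time to complete epithelisation and rate of healing as "both assessed from photographs by masked observers". Section 4.6.5 repeats this in general terms: "All observations will be based on 'blind' assessment". It adds that the ulcer will "be measured by masked observers in another site using the PUSH" tool.

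**Clinical determination.** Section 4.7 says: "The complete healing of ulcer will be determined clinically as complete closure of epithelium of the skin which will be photographed for verification". It does not name the person who makes the call, the person who verifies the photograph, or whether the verifier is masked.

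**Knowledge of allocation.** Under section 4.6.3, "the trial arm and a unique study number will be assigned and revealed to the local clinician". Section 4.5.1 describes a walker boot covering the lower leg in one arm and rubber footwear in the other.

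**What healing ends.** Section 4.7: "Patients will be followed up weekly for 8 weeks or until ulcer completely heals, whichever is earlier". Section 4.6.5: "photographs of ulcers will be taken at baseline and after every 2 weeks until the ulcer heals or at 8 weeks, whichever is earlier". The satisfaction questionnaire (QUEST 2.0) is given once, at healing or at 8 weeks. In the case record form (Appendix 3) the last follow-up column is for week 8 or for complete healing, so a healed participant has no separate week-8 entry.

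**The concern.** Two sections promise that every healing observation is made by someone who does not know the arm. A third lets the key event, complete closure, be decided at the visit. Nobody who sees the patient with the device can be masked, so the decision that fixes the healing date may depend on the arm.

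The decision also controls how much more data are collected. A late or missed call is partly self-correcting, because the participant stays in follow-up and the next 2-weekly photograph can show closure. A call made too early removes the participant from the sequence that would have shown the error. At stake are the pilot estimates of time to healing, area reduction and 8-week status. To a lesser degree the step counts are affected too: section 4.9 analyses cumulative steps over the assessment period, and that period would be cut short. Piloting trial methods and measurements is an objective in its own right (section 3), so an unclear masking procedure could be carried into the larger trial.

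**Working it through.** The protocol gives no figure for this point. The main check is a comparison of the text, followed by an illustration.

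**1. Who defines healing?**

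| Question | Sections 1.8 and 4.6.5 | Section 4.7 |
|---|---|---|
| Basis | Photographs | Clinical determination, with a photograph for verification |
| Assessor | Masked observers, in another site | Not named; a clinical call needs someone with the patient |
| Role of the photograph | Source of the measurement | Check on a decision already made |
| Which prevails if they differ | Not stated | Not stated |

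Observers at another site reading images cannot make a clinical determination, so these are two different acts by different people. That the clinical call is unmasked is an inference. It rests on section 4.6.3 (the arm is revealed locally) and on the visible difference between the devices.

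**2. What happens after a wrong call of healed?** There are three possible sequences, and the protocol does not choose between them.

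- The masked reader sees the photograph before exit and rejects the call. Follow-up goes on and nothing is lost.
- The masked reader sees it after exit and rejects the call. Healed status at that visit is corrected, but there is no later photograph, so healing time, later area and 8-week status are unknown.
- The clinical call stands. The participant counts as healed on the wrong date.

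**3. Illustration.** Inputs: 150 participants allocated 1:1 (sections 4.4 and 4.6.3), so 150 / 2 = 75 per arm; healing of 70%, the control figure in section 4.4, taken as true in both arms. Assumptions that are not in the protocol: a fraction f of the boot-arm ulcers that are truly unhealed is called healed, and no such error occurs in the control arm.

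Apparent boot-arm healing if nothing is corrected = 0.70 + 0.30 × f

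| f | Apparent healing | False difference | Participants of 75 | False difference if half the calls are rejected |
|---|---|---|---|---|
| 0.10 | 0.70 + 0.03 = 0.73 | 3 points | 75 × 0.03 = 2.25 | 1.5 points |
| 0.20 | 0.70 + 0.06 = 0.76 | 6 points | 75 × 0.06 = 4.5 | 3 points |
| 0.30 | 0.70 + 0.09 = 0.79 | 9 points | 75 × 0.09 = 6.75 | 4.5 points |

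If the masked reader rejects every false call, the false difference in healed status at that visit is zero. If those participants have already left, the same 3%, 6% or 9% of the boot arm has no later outcome. Bias and missing data are therefore alternatives for any one participant and must not be added together. An ulcer called healed early that does close by week 8 leaves the 8-week proportion unchanged but has the wrong healing date; the table does not capture that error.

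**The case against.** The strongest reply is that the sections can be read together: the clinical call is the field step that prompts a closure photograph, and the masked observers then read it. The verification photograph is in the very sentence at issue, images are captured on tablets, and section 5.4 says the database can transfer them, so reading before exit is feasible. Follow-up is also said to run until the ulcer heals, not until local staff declare it healed. This reading is possible, but the protocol does not state it. It leaves open who verifies, when, and which reading counts. Those are rules of conduct, and no later analysis plan can supply photographs that were not taken.

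Some stronger readings are tempting but unsupported:

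- A reader might infer that a biased call can never be corrected. The verification photograph allows rejection for that visit, and only the later course is at risk.
- A reader might infer that masked reading takes place only after exit. The order is not given.
- A reader might infer that satisfaction data are lost. QUEST is given once, and a false call merely brings it forward.
- A reader might infer that the main conclusion is threatened. Comparing healing rates is a secondary objective (section 3), section 4.4 does not expect to observe a difference, and section 4.9 relies on intervals and not on hypothesis tests. The area-reduction measure named in section 4.9 would also change little if a nearly closed ulcer were called closed.

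It is also fair that the error rates above are invented and one-directional.

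**Conclusion.** The inconsistency is real and should be resolved. Sections 1.8 and 4.6.5 promise masked assessment of healing, and section 4.7 attaches the healing event, and with it the end of data collection, to a clinical determination. Precedence and timing of the masked reading are not stated.

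The consequence is possible detection bias, or missing later outcomes, in the pilot healing estimates, with a shortened pedometer period and an early satisfaction score for the participants concerned. Its size is unknown. The range of 3 to 9 points, about 2 to 7 of 75 participants, depends wholly on assumed error rates of 10% to 30% in one arm and no correction. It falls to zero for healed status if masked reading catches every false call. The conclusion also rests on the inference that whoever makes the clinical call can see the device. This is a moderate point about a secondary objective, worth correcting because the remedy is cheap and the procedure is meant to inform a larger trial.

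**What to change.** Reconcile sections 1.8 and 4.6.5 with section 4.7:

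1. State that the masked photograph reading defines healed status and healing date, and that the local clinical call only triggers a photograph.
2. Then choose one of two rules. Either obtain masked confirmation before outcome follow-up ends, or continue the scheduled 2-weekly photographs to week 8 for every participant. In both cases this is for outcome measurement only and says nothing about which device is worn after clinical closure.
3. If photographs continue, give the case record form a week-8 entry separate from the entry at healing, and state how the pedometer period and the QUEST date are set.

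A requirement that closure be sustained at a later visit is not needed to resolve this point.

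**Cost.** The first rule needs a prompt turnaround from the masked readers. The second adds photographs for healed participants: at most four (weeks 2, 4, 6 and 8) for an ulcer called closed at week 1, and one for an ulcer called closed at week 6. Masked readers, tablets and a weekly visit schedule are already in the plan, although healed participants would have to be seen at visits they would otherwise have missed.

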5.1.4 Withdrawal

Participants are free to withdraw at any time as explained to people in the information provided. The participant may withdraw in two ways:

- 1. Does not wish to continue in the intervention, but happy to contribute follow-up data
- 2. Does not wish to continue to contribute follow-up data

There will be a notice of withdrawal form on the data collection tablet for people in the second group above but people who are in the first group will continue to contribute data but their withdrawal from participation in group activity will be noted.

As this is a feasibility plus trial, there will be no data monitoring committee and no interim analysis. Rather, the study managers will monitor accruing data as a check on quality and so that action may be taken if data are incomplete.

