5.7 Gantt Chart

	Apr	May	Jun	Jul	Aug	Sep	Oct	Nov	Dec	Jan	Feb	Mar	Apr	May	Jun	Jul	Aug	Sep	Oct	Nov
Ethics Approval																				
Recruitment of staff																				
Training of staff																				
Line listing & tracing																				
(DM) and leprosy																				
patients																				
Recruitment of																				
patients																				
Intervention																				
Follow-up																				
Qualitative interview																				
Data cleaning																				
Analysis																				
Report writing &																				
Publication																				
Contingency																				

Ethics section:

SECTION 2

Risk and	What are the potential risks to the participants? Consider social and emotional
benefits	risks as well as more obvious physical risks.
Schents	There are no additional risk associated with participating in the study. The treatment
	method of removable walker works the same way as total contact cast which has
	been in practice for ulcer care in leprosy. Patients may develop skin abrasion due to
	ill-fitting walker boots. However, removable walkers used in this study is considered
	safe as it comes with soft inner lining to prevent skin abrasions. We expect that
	application of removable cast in the community will help ulcer heal faster without
	requiring for hospital admission.
	What is your risk management plan?
	If patient develops skin abrasions, we will discontinue the removable walker boot
	and patient will be called to hospital for medical care which will be as per standard
	protocol of the Leprosy Mission Trust India hospital in Champa.
	What will be the companyation for unexpected risks?
	There are no compensation planned for expected risks
	There are no compensation planned for expected fisks.
	What are the potential benefits to the participants?
	In routine care micro-cellular rubber footwear is provided for patients with
	insensitive foot irrespective of presence of ulcer. The treatment provided in this
	study are standard care for ulcer management in leprosy. Regular monitoring of
	ulcers and feedback to patient will help in healing of ulcers.
Safety and	Does this study involve invasive or hazardous procedures, ionizing radiation or
other	hazardous substances (including radiological imaging, vein puncture, or intimate
	physical examination)?
controls	
	No
Informed	What will be the procedure for seeking informed consent from research

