related to ulcer	t/IN	t/IN	t/IN	t/IN		
If yes, specify						
Adverse events	V /N	V /N	V/N	V /N		
related to device	t/IN	T/IN	1/11	T/IN		
If yes, specify						

User satisfaction with off-loading devices

(at completion of 8 weeks or complete healing of ulcer)

Quebec User Evaluation of Satisfaction with Assistive Technology (QUEST) 2.0

1	2	3	4	4		5			
not satisfied at all	not very satisfied	more or less satisfied	quite sati	quite satisfied			very satisfied		
How satisfied a	ASSISTIVE DEVICE								
1, the dimension	ns (size, height, l	ength, width) of	vour						
assistive device	?		,						
Comments:				1	2	3	4	5	
2. the weight of	your assistive de	evice?							
Comments:	-			1	2	3	4	5	
3. the ease in ad	ljusting (fixing,	fastening) the par	rts of						
your assistive de	evice?								
Comments:				1	2	3	4	5	
4. how safe and	secure your ass	istive device is?							
Comments:				1	2	3	4	5	
5. the durability	y (endurance, res	istance to wear) o	of your						
assistive device?	?								
Comments:				1	2	3	4	5	
6. how easy it is	to use your assis	stive device?							
Comments:				1	2	3	4	5	
7. how comfort	able your assistiv	ve device is?							
Comments:				1	2	3	4	5	
8. how effective	your assistive d	evice is (the degr	ee to						
which your devi	ce meets your ne	eds)?							
Comments:				1	2	3	4	5	

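### Section 4.7 ends follow-up when a complication affects device wearing, so healing, satisfaction and adherence are estimated on a group selected by poor outcome; the direction of the resulting bias cannot be foreseen

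*Protocol*

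**What the plan says.** Protocol section 4.7 sets the follow-up schedule: "Patients will be followed up weekly for 8 weeks or until ulcer completely heals, whichever is earlier". It then makes an exception for complications, giving as examples "worsening of existing ulcer, skin abrasions due to friction or sever swelling to the foot or leg". Of these participants it says "they may be considered as censored if it affects the wearing of the off-loading device and will not be continued for follow-up", and they are referred to hospital. The rule is worded for both arms.

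Four other places bear on it:

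- **Section 5.1.4 (Withdrawal)** recognises a participant who "Does not wish to continue in the intervention, but happy to contribute follow-up data", and states that "people who are in the first group will continue to contribute data".
- **Ethics section, risks and benefits (after the Gantt chart in 5.7)** says "Patients may develop skin abrasion due to" ill-fitting boots, and gives the management plan as "If patient develops skin abrasions, we will discontinue the removable walker boot". That sentence has neither the discretion nor the condition found in 4.7.
- **Section 4.6.5 and Appendix 3** schedule the QUEST questionnaire once, "at completion of 8 weeks or complete healing of ulcer". No assessment is set for an earlier exit.
- **Sections 4.6.5 and 4.9** define the other outcomes: time to complete epithelisation and percentage area reduction over 8 weeks for healing, and weekly pedometer readings for adherence. Adherence is summarised as mean cumulative steps from the foot device and as the wrist-foot difference.

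**The concern.** A worsening ulcer is the reverse of the healing outcome, and an abrasion is a harm that the protocol itself links to the boot. Censoring treats the people removed as if they would have gone on to heal at the same rate as those who remain. That is hard to defend when the reason for removal is that the ulcer or the skin has got worse.

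The rule also ends data collection, so a later analysis plan cannot repair it. The week-8 ulcer area, the later pedometer readings and the satisfaction score would not exist for the people in whom wearing the device failed. Adherence and acceptability are the primary objectives, and failure of wearing is one of the things the trial needs to measure.

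The wording is permissive and gives no criterion, so similar cases could be handled differently between sites or arms. Section 4.6.3 reveals the allocation to the local clinician, and masking is described only for the ulcer assessment.

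**Working it through.** **The plan's own figure.** Section 4.4 gives a 95% CI of 0.42 to 0.58 for adherence of 0.5 with n = 150. Check: 0.5 ± 1.96 × √(0.25/150) = 0.5 ± 0.080, which reproduces. If 10% were dropped, n = 135 and the interval is 0.5 ± 1.96 × √(0.25/135) = 0.5 ± 0.084, or 0.416 to 0.584. Precision hardly changes; the problem is selection.

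**Inputs.** True 8-week healing is 70% (the control rate in section 4.4), applied to both arms so that the true difference is zero. The fraction of an arm dropped, c, and the fraction of those who would have healed anyway, h, are assumptions, because the protocol gives neither.

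**Healing among those retained** = (0.70 − c·h)/(1 − c).

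- c = 10%, h = 0: 0.70/0.90 = 77.8%, inflated by 7.8 points.
- c = 10%, h = 0.5: (0.70 − 0.05)/0.90 = 72.2%, inflated by 2.2 points.
- c = 5%, h = 0: 0.70/0.95 = 73.7%.
- c = 20%, h = 0: 0.70/0.80 = 87.5%.

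**Between-arm difference under a true null, h = 0:**

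| Dropped, boot | Dropped, control | Boot | Control | Difference (points) |
|---|---|---|---|---|
| 10% | 5% | 77.8% | 73.7% | +4.1 |
| 15% | 5% | 82.4% | 73.7% | +8.7 |
| 10% | 10% | 77.8% | 77.8% | 0 |
| 5% | 10% | 73.7% | 77.8% | −4.1 |
| 5% | 15% | 73.7% | 82.4% | −8.7 |

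A Kaplan-Meier estimate, with healing spread evenly over 8 weeks and dropped participants censored at week 2 or week 4, gives +3.4 to +3.9 points for 10% against 5%. Censoring in a time-to-event analysis therefore does not remove the bias.

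**Could the analysis simply count dropped people as not healed?** With c = 10% and h = 0.5 that gives 0.70 − 0.05 = 65%, against a true 70% and 72.2% among those retained. Neither convention recovers the truth without the follow-up.

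**Satisfaction.** Assume a mean QUEST score of 4.0 in those retained and 2.5 in those dropped. With 10% dropped the full mean is 0.9 × 4.0 + 0.1 × 2.5 = 3.85, reported as 4.0.

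**Adherence, two measures, two directions.**

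- Foot/wrist ratio: assume 0.50 in those retained and 0.20 over the full period in those dropped. With 10% dropped the full value is 0.9 × 0.50 + 0.1 × 0.20 = 0.47, read as 0.50: inflated.
- Mean cumulative foot steps: if 10% have records ending at week 3 of 8, the mean relative to 8-week records at the same step rate is 0.9 + 0.1 × 3/8 = 0.9375, about 6% lower: truncated.

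**The case against.** The strongest reply is that this is a feasibility trial. Healing is a secondary objective, and section 4.4 expects no observable healing difference. Harm would not go unseen either: Appendix 3 has adverse-event fields for ulcer and device at each two-weekly assessment, and boot users are interviewed at 2 to 4 weeks. These points lower the stakes for the healing comparison. They do not supply the missing QUEST scores or pedometer readings, which serve the primary objectives, and the healing rates are still meant to inform a larger trial.

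A second reply is that the illustrations are severe: an abrasion that interrupts wear does not mean the ulcer cannot heal. That stands, and it is why 72% is shown beside 78%.

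Four stronger readings are tempting but not supported:

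- **That the bias favours the boot on every outcome.** The rule covers both arms and its first trigger is ulcer worsening. If the boot works, worsening would be commoner in controls and the healing bias would run against the boot. Truncated cumulative steps would also lower the arm that loses more people.
- **That section 5.1.4 says the opposite of 4.7.** It concerns participants who choose to stop; 4.7 concerns complications leading to referral. The handling is inconsistent, but it is not a direct contradiction.
- **That unmasked staff make the censoring decision.** Section 4.7 does not say who decides.
- **That nobody who cannot tolerate the device rates it.** Someone who stops wearing it but stays in follow-up still completes QUEST.

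**Conclusion.** The concern holds as one of informative censoring with lost follow-up, at undefined discretion, affecting all three main outcomes. Its sign is not determined: it depends on which arm loses more people, on how many of them would have healed, and on the adherence measure.

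As to size, losing 10% of an arm inflates its healing rate by roughly 2 to 8 points, and unequal losses of 10% against 5% can create a difference of about 4 points where none exists. These figures rest on the 70% healing rate in section 4.4 and on assumed complication rates, and the upper values assume that none of those dropped would have healed. A bias of unknown sign is no safer for planning a main trial than one of known sign, and data not collected cannot be recovered, so the rule should be changed before it is applied.

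**What to change.** Amend section 4.7 so that stopping the device and stopping data collection are separate events:

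- Keep participants who stop the device for a complication in outcome follow-up until healing or week 8, whichever is earlier. Follow-up need not extend past healing.
- Count them as not healed unless masked photographs show healing.
- Collect QUEST and a pedometer reading when the device is stopped.
- Report adherence over the full assessment period, with stopping directed by the study identified separately from the participant's own non-use.
- Censor only at loss to follow-up or withdrawal of consent for data.

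Reconcile section 4.7, section 5.1.4 and the risk management text in the ethics section. No view is taken here on when a device should be stopped.

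The cost is amendment wording, which section 5.2 requires to go to the ethics committees, and a few continued visits. Some travel is involved, notably in Nepal, where participants may come from the Biratnagar and Butwal clinics but be referred to Anandaban Hospital.

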4.8 Qualitative study

User experience on removable walker boot will be explored through semi-structured walking interviews. A random sample of patients in the intervention arm of the trial, stratified by gender and age group, will be sampled. Recruitment will be undertaken when the participant joins the trial. The walking interview will be arranged for 2-4 weeks after they receive the walker boots to allow time for the interviewee to experience living with the walker boot. We will recruit until data saturation – estimate fifteen patients from each site. The researcher will arrange to spend up to half a day with each patient. They will be asked to show the researcher around their household and locality as far as they are able to reach without transport and during this walk, explain how use or not of the device affects their ability to undertake daily routines and mobility. They will be asked about their experiences of using the device, challenges they meet in using the device and how they negotiate challenges related to using removable walker boots. They will also be asked about what modifications can be made to improve its effectiveness in off-loading at the same time as to improve adherence. The researcher will audio record the interview and take field notes. Interviews will be transcribed and translated. Fieldnotes will be typed up and

expanded after the walking interview. Data from all sites will be combined for thematic analysis, whilst paying attention to differences in context for interviewees from the different sites.

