4.9 Trial analysis plan

The adherence to off-loading devices in the intervention will be based on the number of steps taken by the patient during the assessment period. The mean cumulative steps taken (confidence limits) will be measured using the foot device. We will also measure and compare the difference between wrist and foot between intervention and control. The mean user satisfaction score between the intervention and control group will be tested using t-test. Higher the user satisfaction score indicates greater the satisfaction with the off-loading device. The healing rate between the groups as percentage reduction in the ulcer area per unit time (8 weeks) will be compared between the two groups using methods we have used before. Our statistical philosophy is based on observed standards and confidence/credible intervals and not on hypothesis testing.(34)

5 Governance, Ethics, data collection and security

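### Section 4.7 lets follow-up end when a complication, including a worsening ulcer, affects device wear, so satisfaction, later adherence and later healing data are lost selectively

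*Protocol*

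**What the plan says.** Section 4.7 plans weekly follow-up to healing or 8 weeks. It then lists worsening of the ulcer, friction abrasions and severe swelling as complications, and says of participants who develop them that "they may be considered as censored if it affects the wearing of the off-loading device and will not be continued for follow-up". They are referred to hospital, and no further study assessment is named.

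The outcomes that depend on follow-up are scheduled as follows.

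- **Satisfaction (QUEST 2.0).** Section 4.6.5 takes it "at complete healing of ulcer or at 8 weeks from recruitment, whichever is earlier". The form in Appendix 3 agrees: "at completion of 8 weeks or complete healing of ulcer". There is no early-exit assessment.
- **Healing.** Section 4.6.5 plans photographs every 2 weeks. In section 4.9 the "percentage reduction in the ulcer area per unit time (8 weeks) will be compared between the two groups". The last ulcer visit on the form is at week 8 or at healing.
- **Adherence.** Pedometers are read weekly. Section 4.9 states: "The mean cumulative steps taken (confidence limits) will be measured using the foot device". Section 4.6.5 also compares the arms on steps per day and on the difference between the two pedometers.

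Section 5.1.4 treats people who stop the intervention by choice differently: "people who are in the first group will continue to contribute data", provided they agreed to give follow-up data.

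**The concern.** The rule governs what data are collected, and its trigger is not neutral. A worsening ulcer is itself a poor healing result. An abrasion or swelling that prevents wear bears directly on adherence and acceptability, which are primary objectives. The rule therefore permits follow-up to end in the participants from whom a feasibility study of this device has most to learn.

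Treating them as censored in a time-to-healing analysis assumes that they would have gone on to heal at the same rate as those still under observation. That is hard to defend when the reason for censoring is that the ulcer got worse. For QUEST, the arm mean comes only from people who reached healing or week 8.

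The consequence reaches beyond this study. Section 3 links the healing rates to size calculations, so inflated rates and satisfaction scores would carry into the design of the next trial.

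**Working it through.** **1. Plan's own figure.** The protocol gives no complication or stop rate, so there is no stated figure to reproduce on this point. The inputs taken from it are the visit schedule, 150 participants allocated 1:1 (about 75 per arm) and the 70% control healing rate in section 4.4.

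**2. What one stopped participant loses.** Pedometer readings fall at weeks 1 to 8 and follow-up photographs at weeks 2, 4, 6 and 8. A stop after week w loses 8 − w readings and every photograph after w.

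| Stop after week | Pedometer readings lost (of 8) | Photographs lost (of 4) | Week-8 area | QUEST |
|---|---|---|---|---|
| 1 | 7 | 4 | lost | lost |
| 3 | 5 | 3 | lost | lost |
| 5 | 3 | 2 | lost | lost |
| 7 | 1 | 1 | lost | lost |

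**3. Effect on each adherence measure.** The cumulative foot-device sum ends at the stop and so covers fewer weeks. Steps per day need not fall because of the stop, but they describe only the time before it. The difference between the two pedometers likewise omits the time after it.

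**4. QUEST, illustration.** Assume k of 75 are stopped and would have scored d points below the rest on the 1-5 scale. The observed arm mean is then too high by (k/75) × d.

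| k | d = 1 | d = 2 |
|---|---|---|
| 4 | 4/75 = 0.05 | 0.11 |
| 8 | 8/75 = 0.11 | 0.21 |
| 15 | 15/75 = 0.20 | 0.40 |

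**5. Healing, illustration.** Assume that:

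- true 8-week healing is 70%, so 0.70 × 75 = 52.5 heal;
- the k stopped participants are censored at week 3 and would not have healed;
- the other n = 75 − k heal at constant hazard h = −ln(1 − 52.5/n)/8;
- time to healing is summarised by Kaplan-Meier.

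The number healed by week 3 is H3 = n(1 − exp(−3h)). The apparent 8-week healing is 1 − (1 − H3/75) × (n − 52.5)/(n − H3).

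| k | n | h per week | H3 | Apparent healing | Excess over 70% |
|---|---|---|---|---|---|
| 4 | 71 | 0.168 | 28.1 | 1 − 0.625 × 0.431 = 73.0% | 3.0 points |
| 8 | 67 | 0.191 | 29.3 | 1 − 0.610 × 0.384 = 76.6% | 6.6 points |
| 15 | 60 | 0.260 | 32.5 | 1 − 0.567 × 0.273 = 84.5% | 14.5 points |

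For k = 4, 8 and 15, the excess is 3.7, 7.9 and 16.8 points with censoring at week 1, and 2.1, 4.7 and 10.8 points with censoring at week 5.

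**6. Does anything restore the data?** Section 5.1.4 covers people who choose to stop, not those stopped under 4.7. The ethics section after 5.7 discontinues the boot for abrasions and calls the patient to hospital, without mentioning study follow-up. The interviews in section 4.8 take place early ("The walking interview will be arranged for 2-4 weeks after they receive the walker boots"), with an estimated fifteen boot users per site. They cannot stand in for a satisfaction score compared between arms.

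**The case against.** The other side has real points, and most limit the size of the concern.

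- **Stopped participants do not vanish.** The form records ulcer-related and device-related adverse events, with detail, at each two-weekly assessment, and earlier readings and photographs are kept. This stands: the type and frequency of problems up to the stop can be reported. It supplies neither a satisfaction score nor anything after the stop.
- **Earlier photographs could inform a healing rate.** Section 4.9 speaks of reduction per unit time and leaves the method to earlier practice. A reader might infer that these participants must drop out of the healing-rate comparison. The text does not go that far. A rate from truncated data would still miss the later course of a worsening ulcer.
- **The wording is discretionary.** A reader might take censoring as automatic, but the rule only permits it. Discretion does not remove the problem, because the criteria are loose.
- **Who decides is not stated.** Under section 4.6.3, "the trial arm and a unique study number will be assigned and revealed to the local clinician", and the boot is visible, so staff who know the arm are likely to decide. That is inference, because 4.7 names nobody.
- **The illustrations are assumed.** Entry is restricted to uncomplicated, non-infected ulcers, and nothing in the protocol supports 15 of 75 being stopped, or none of them healing after referral. Section 4.4 does not expect to show a healing difference. This stands as a limit on the numbers, not on the collection rule.
- **Coding device steps as zero after a clinician removes the boot is debatable.** It would mix medical contraindication with non-adherence. This stands, and the fix below does not impose it.

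**Conclusion.** The point holds. As written, section 4.7 permits outcome-related loss of QUEST, the week-8 ulcer area and all later pedometer and photograph data, and nothing else in the protocol restores them. Satisfaction and healing are likely to look better than they were, and the adherence measures do not describe the time after the stop.

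Confidence is high on the text and low on the size. The 73.0% to 76.6% apparent healing against 70% true healing assumes 4 to 8 of 75 stopped at week 3, with none healing; 84.5% is an extreme case. The QUEST shifts of 0.05 to 0.40 points rest on equally assumed inputs.

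A reader might also infer that the rule favours the boot. The documents do not support that. The rule applies to both arms and no complication rates are given. The ethics section names ill-fitting boots as a cause of abrasion, so unequal stopping is possible, but the between-arm direction is not fixed.

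This should be changed before follow-up is under way, because data not collected cannot be recovered at analysis.

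**What to change.** In section 4.7, delete the wording that treats these participants as censored and ends their follow-up. Keep device discontinuation and referral for treatment unchanged. Then add the following.

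1. Take QUEST when the device is stopped, and add this time point to section 4.6.5 and Appendix 3.
2. Where the participant agrees, continue the scheduled two-weekly photographs and weekly body-worn pedometer readings to healing or week 8. This follows the principle in section 5.1.4 that people who stop the intervention still contribute data. That section sets no pedometer or photograph schedule, so 4.7 must state it.
3. Record the date of the stop and that it was clinician-directed. Adherence can then be reported both up to the stop and over the full 8 weeks, with stops for complications told apart from non-adherence by choice.

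The cost is one wording change, one extra administration of the 8-item QUEST and one form field for the stop. Each stopped participant also needs at most 7 weekly contacts that are already in the schedule. Some would take place at the referral hospital, where step counts are not directly comparable with walking at home and should be identified as such.
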